# "Fast track" surgery on patient undergoing minimally invasive gynaecologic procedure: a randomized clinical trial

# **Introduction:**

[figure not shown]
The concept of "enhanced recovery" was developed by American cardiologists in the 1950s to improve patient rehabilitation after a myocardial infarction. In 1995, this concept was extended to colonic surgery by Kehlet et al. who developed a perioperative multimodal strategy currently known as 'Fast track' (FT), or " Enhanced recovery after surgery ' (ERAS).¹ This innovative concept suggests including the combination of minimally invasive surgery, analgesia optimization, early oral refeeding and rapid mobilization of patients which reduces pain and organic dysfunction induced by surgical stress. This concept, increasingly applied worldwide in colorectal surgery, has also shown efficiency by reducing hospitalization lenght.².³ Gynaecological surgery, similar to colonic surgery in many ways, has very little explored this concept.

#### The concept of "Fast track" or "Enhanced recovery after surgery":

FT is a global perioperative approach aiming to optimize patient care by early rehabilitation. The objectives are to reduce post-operative pain and organic dysfunction induced by surgical stress. This strategy facilitates recovery and comfort of patients while decreasing morbidity, hospitalization length and costs. This multimodal approach requires a close and well codified multidisciplinary collaboration in between surgeons, anaesthetists and the nursing team. The key elements of the program include preoperative patient information and education, lack of digestive preparation, perioperative water balance, analgesia optimization, early oral refeeding and rapid mobilization of patients. These elements can be classified into four subgroups in terms of overall support: 1) patient information and education, 2) preoperative, 3) perioperative and 4) postoperative (Figure 1).

Figure 1

The patient, at the centre of this concept, is a major actor. Appropriate patient information and education as well as patient motivation are necessary. Indeed, the patient needs to adhere and take an active part in order for this approach to be successful. Age does not seem to be a limiting factor to FT participation.

Discharge from hospital and the patients return home require anticipated planning. To guarantee the success of a FT approach, hospital discharge criteria must be established and met as well as a homecare plan must be put into place. Commonly accepted discharge criteria are:

- Lack of organ dysfunction
- Afebrile condition
- Simple effective analgesia
- Normal feeding
- Independent mobility
- Patient consent

The patients social network must be evaluated and support by a health aide or a visiting nurse can be introduced if necessary. Medical follow-up must also be organized beforehand.

# What are the expected benefits of "Fast track" surgery?

FT surgery facilitates the aftermath of surgery and presents an overall benefit for patients, caregivers and the health care system as demonstrated in colorectal surgery.

Overall benefits, out of which we can note:

- Earlier rehabilitation
- Reduced hospitalization length
- Decreased hospital and public health costs
- Patient satisfaction
- Reduced postoperative complications (infections, pulmonary pathologies, ileus, ...)

A preoccupation could be an increase in readmission rate but this hypothesis is invalidated by various studies. 9-11

#### What are the current use and benefits of 'Fast track' in gynaecological surgery?

A recent review of the literature shows that the use of FT setting is only marginal in gynaecological surgery with some 30 publications identified to date in the 'Medline' and 'Ovid' databases as well as the 'Cochrane' library, most of which concern anaesthetic care. Indeed, no study has actually compared FT with conventional setting in gynaecological surgery and a fortiori no controlled randomized trial is found to bring a level of evidence sufficient to its wider implementation. The use of FT programs in gynaecological surgery however appears to be effective in reducing length of hospitalization in abdominal and vaginal hysterectomies as well as in vaginal surgery for prolapse. 12-14 A small-size descriptive study was carried out by Möller and Co and published in  $1998.^{12}$  Thirty-two patients allocated either to abdominal hysterectomy (n = 16) or laparoscopically assisted vaginal hysterectomy (n = 16) benefited from FT setting. The results showed shorter hospitalization for laparoscopically assisted vaginal hysterectomy of 1 day and 2 days for abdominal hysterectomy. These results are encouraging in comparison to the length of hospitalization in classical setting which are usually doubled. Another small-size descriptive study including 41 patients carried out by Ottensen and Co13 and published in 2002 showed postoperative hospitalization of 24 hours after vaginal surgery for utero-vaginal prolapse in a fast track setting with no readmission occurred.

A synthesis of the results published in different studies regarding hospitalization length in FT setting shows a benefit in abdominal hysterectomy by laparotomy (Figure 2). No data was found for hysterectomy by laparoscopic approach.

Figure 2

Hospitalization length in conventional and "Fast track" setting (in days)		
	Conventional setting	"Fast track" setting
Abdominal hysterectomy	3.8  - 5.1 	1.9  - 2.6 
Laparoscopic hysterectomy	1.8  - 3.9 	Not available

In gynaecologic oncology surgery, a FT setting seems to be beneficial in patients operated for ovarian malignancy.  However, a recent Cochrane review showed that there was no evidence from high quality studies to support or refute the use of perioperative enhanced recovery programmes for gynaecological cancer patients. 

The aspects of financial benefit for hospitals and public health have not been assessed. High quality studies evaluating patient satisfaction or benefits in terms of quality of life cannot be found.

Conducting a randomized clinical trial in gynaecological surgery comparing FT and conventional setting in laparoscopic hysterectomy for benign indication, laparoscopy currently being the privileged way of access, is necessary to evaluate FT setting efficiency. The results of such a study could have major impact in perioperative care whilst demonstrating financial benefit for public health and patient satisfaction without changing complication and readmission rates. This is even more relevant in Switzerland, a country with a health care system combining fee for service and universal health insurance coverage, and where national health costs accounted for 11.5% of GDP in 2012 and are estimated at 16.7% of GDP in 2030.

Hôpitaux Universitaires Genève

« Fast track » surgery on patient undergoing minimally invasive gynaecologic procedure : a randomized clinical trial. V2.0 – 2015.09.29

**Hypothesis and objectives:** 

Hypothesis:

The concept of "Fast track" which has proven its effectiveness in colorectal surgery is applicable in

gynaecological surgery.

Perioperative "Fast track" setting is more efficient than conventional setting in laparoscopic

hysterectomy for benign indication.

Objectives:

The main objective of this study is to evaluate effectiveness of the "Fast track" concept in

laparoscopic hysterectomy for benign indication in comparison to conventional setting in terms of

cost and patient satisfaction. Earlier rehabilitation, diminution in hospitalization length and stable

postoperative morbidity (number of thromboembolic events, number of infections, readmission

rate) will be verified.

**Methods:** 

Design:

Randomized control trial: the randomization in two groups will be performed by computer using

block of different sizes (2 and 4) before patient inclusion. Sealed, opaque and numbered

envelopes will be prepared and patients will be included consecutively.

Population:

All patients in our gynaecology department, in whom an indication of total or subtotal

laparoscopic hysterectomy for benign indication with or without adnexectomy has been

established (including robot-assisted interventions), will be proposed this study.

Exclusion criteria:

Patients needing an additional surgical procedure such as a prolapse surgery or urinary

incontinence surgery as well as malignant pathologies will not be included in the study due to

prolonged operative time which could compromise early home return. Non-French speaking

patients will also be excluded from the study due to the necessity of their collaboration in filling a

logbook drawn up in French on a daily basis during their hospitalization.

6

Etude CCER n° 15-103 : Fast Track\_V.2.0-2015.09.29

« Fast track » surgery on patient undergoing minimally invasive gynaecologic procedure: a randomized clinical trial. V2.0 – 2015.09.29

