**Recruitment:** 

During pre-hospitalisation visit where surgical indications are established, eligible patients will

meet a research nurse who will explain the study giving patients oral and written information. If

the patient agrees to participate in the study, she will be included randomly in one of the two

groups after having signed a consent form. She will immediately be informed of her allocation to

the "Fast track" or the control group in order to best prepare her personal perioperative planning.

To increase the number of patients recruited, patients that meet the criteria of the study but who

were not informed during the pre-hospitalisation visit will be contacted by a research nurse after

the weekly colloquium of surgical indications, colloquium where all surgical indications of the

department of gynaecology of the HUG are confirmed.

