#### • Instruments:

- 1) Costs of the two types of setting ("Fast track" and classic) will be compared taking into account hospitalization and ambulatory costs which will be obtained via the patient EDS number as discussed with the medico-information department ([name]). In addition, home care will be accounted for via invoices and family/friends loss of earnings will be calculated based on the number of absent working days. With Switzerland's median wage of CHF 6118 per month in 2012 and approximately 21 working days per month, we can estimate a median wage of CHF 291 per working day.
- 2) Patients satisfaction in both groups will be evaluated via a satisfaction questionnaire on their day of return home and at their follow-up visit one month after surgery.
- 3) Patients will be given a logbook questioning them on their pain awareness, their digestion and their mobilisation during their hospital stay.
- 4) Morbidity during the first month post-operation (i.e. readmission rate, number of infections and number of thromboembolic events) will be evaluated via the medical staff case report form.

A medical staff case report form containing their detailed clinical pathway will be used to verify patient's adhesion rate at each stage of the protocol.

A care map for each group will be used by the medical staff as a synopsis of the clinical pathway and will have to be signed by each medical intervener (nurse, gynaecologist and anaesthetist).

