#### Collaboration between surgeons, anaesthetists and caregivers

All interveners of the gynaecology department will be informed orally by the main investigator during an information session and by written. A copy of the study protocol will be sent by e-mail.

Anaesthetists will also be informed orally by the main investigator and a representative who already has experience in the "Fast track" concept will be officially appointed. A copy of the study protocol will be sent by e-mail.

[figure not shown]
Finally, the nursing team will also be informed in the same way and a representative will also be appointed.

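### Blocks of 2 and 4, printed in a protocol e-mailed to staff of an open single-department trial, let a recruiter who follows the sequence guess about 72% of allocations; withhold the sizes and regenerate the list without size 2

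*Combined protocol and SAP*

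**What the plan says.** **Allocation list.** Methods, Design: two groups, randomized by computer using "block of different sizes (2 and 4) before patient inclusion". The proportion of blocks of each size is not given, and no stratification is mentioned, so there appears to be a single list.

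**Concealment.** The same paragraph provides for envelopes that are "Sealed, opaque and numbered" and says "envelopes will be prepared and patients will be included consecutively". Under Recruitment, a research nurse informs the patient, and allocation follows signed consent.

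**Disclosure.** Recruitment: "She will immediately be informed of her allocation to" one group or the other. Under Instruments, each group has its own care map, signed by the nurse, gynaecologist and anaesthetist involved, so past allocations are visible to staff.

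**Circulation of the protocol.** The Logistics section on collaboration between the professions states: "All interveners of the gynaecology department will be informed orally by the main investigator during an information session and by written". This is followed by "A copy of the study protocol will be sent by e-mail". The same e-mail provision is repeated for the anaesthetists, and the nursing team is to be informed in like manner.

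**Who is recruited.** One gynaecology department. All patients with the indication are to be offered the study, but Logistics, Calendar expects to recruit half of those eligible.

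The documents do not withhold the block sizes from recruiters. They do not name who generates the list or opens the envelopes, and they do not describe central allocation or a log of patients not approached.

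**The concern.** A sealed envelope stops anyone reading the next allocation but not inferring it. With blocks of 2 and 4 the running difference between the arms never exceeds 2 and returns to zero every few patients. Whoever has seen the earlier allocations can therefore bet on the arm that is behind.

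A recruiter with such a forecast could let it influence whom to approach, or when. The primary outcome is total cost, including home care and relatives' lost earnings. Expected surgical complexity and home support plausibly affect that cost and may be known before a patient is approached. Selection on such features would make the arms differ at entry. Intention-to-treat analysis does not correct this, the planned t-test has no stated adjustment, and the baseline factors named under Type of analysis (age, BMI, hypertension, diabetes, smoking) include neither feature.

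**Working it through.** **1. The plan's own figure.** Sample size gives 85 per arm for a difference of 0.5 SD, two-sided 0.05, power 90%. The normal formula is 2 × (1.960 + 1.282)² / 0.5² ≈ 84.1, rounded up to 85 per arm and 170 in total. The t-test gives power 0.900 at 85 per arm. The figure reproduces and does not depend on this point.

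**2. Exact predictability.** Let p be the share of blocks of size 2 (not stated, so varied from 25% to 75%). The mean block length is L = 2p + 4(1 − p). The observer bets on the lagging arm and tosses a coin when the arms are level.
- Block of 2: expected correct guesses 0.5 + 1 = 1.5. Positions with the arms unequal: 1.
- Block of 4: expected correct guesses 0.5 + 2/3 + (1/3)(2) + (2/3)(1.5) = 2.833. Positions with the arms unequal: 1 + 1/3 + 1 = 2.333.
- Share correct = [1.5p + 2.833(1 − p)] / L.
- Share guessable better than chance = [p + 2.333(1 − p)] / L.
- Share certain = (1 − p) × (1/3) × 2 / L. A difference of 2 arises only inside a block of 4, and it fixes the next two allocations.

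The share with probability at least 0.80 was simulated: 170 patients, with the observer knowing the sizes and updating after every allocation.

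| Share of 2-blocks | L | Correct | Guessable (each with probability ≥ 0.75) | Probability ≥ 0.80 | Certain | Coin toss |
|---|---|---|---|---|---|---|
| 25% | 3.5 | 71.4% | 57.1% | 44.4% | 14.3% | 42.9% |
| 50% | 3.0 | 72.2% | 55.6% | 55.5% | 11.1% | 44.4% |
| 75% | 2.5 | 73.3% | 53.3% | 53.3% | 6.7% | 46.7% |

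Simulating all columns agrees with the exact values to within 0.1 to 0.2 percentage points. With equal mixing, about 94 of 170 allocations are guessable and about 19 are certain. Fixed blocks of 4 would give 71% correct and 33% certain, so mixing 2 with 4 reduces certainty but not average predictability.

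Betting on the lagging arm requires no knowledge of the block sizes and scores the same 72% as the optimal guess. Knowing the sizes adds confidence: it shows which guesses are certain.

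**3. Alternatives, same observer.**
- Blocks of 4, 6 and 8, equal mix: 68% correct, 25% with probability ≥ 0.80, 2% certain.
- Big stick, limit 6: 7.7% of allocations are forced and the rest are coin tosses, so 0.077 + 0.5 × 0.923 = 54% correct.

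**4. Illustration only.** Suppose every enrolment is steered on the guess, shifting expected cost by s SD one way or the other. With correct-guess rate g, the arm difference is biased by 2s(2g − 1). Sample size implies an SD of 1400 / 0.5 = CHF 2800. With s assumed at 0.1 to 0.2:
- Blocks 2/4 (g = 0.72): 0.088 to 0.176 SD, about CHF 246 to 493.
- Blocks 4/6/8 (g = 0.68): 0.072 to 0.144 SD, about CHF 202 to 403. The reduction is 1 − 0.36/0.44 = 18%.
- Big stick (g = 0.54): 0.016 to 0.032 SD, about CHF 45 to 90.

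**5. Cost in power.** t-test power at 0.5 SD is 0.8999 for 85/85, 0.8997 for 87/83 and 0.8995 for 88/82, the widest split that limit 6 permits. Simple randomization would give about 0.898.

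**The case against.** The plan has real safeguards. The list is made before inclusion, the envelopes are opaque and numbered, consent precedes allocation, inclusion is consecutive, and every patient with the indication is to be offered the study. Contacting missed patients after the weekly colloquium widens coverage, and nothing in that text gives the nurse discretion over whom to call. The expected recruitment of one in two may simply reflect refusals. All of this stands as mitigation. None of it prevents inference: consecutive inclusion orders those who enrol, and does not control who is approached or when.

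Three stronger readings are tempting and are not supported.
- **Most allocations are known in advance.** At most about one in seven is certain, and well over 40% are coin tosses. Even the statement that a majority are predictable depends on the threshold: at 0.80 the share falls to 44% if a quarter of blocks have size 2.
- **Surgeons at large can steer enrolment.** Recruitment is given to research nurses, and the list linking names to study numbers is restricted to investigators and research nurses. The calculated rates need an observer who follows the whole sequence, which is most realistic for those nurses.
- **The cost comparison will be wrong by some hundreds of francs.** That figure needs an assumed shift and steering at every enrolment. No text suggests that staff would do this.

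**Conclusion.** The point holds as an avoidable weakness in allocation concealment. It is not evidence of bias. For any share of 2-blocks between 25% and 75%, an observer who knows the sizes and tracks all earlier allocations is right 71% to 73% of the time, against 50% by chance, and 53% to 57% of allocations can be predicted with probability at least 0.75. This rests on the single unstratified list that the text implies and on complete tracking, which immediate disclosure in one department makes feasible. The size of any resulting bias cannot be derived from the documents. With no stratification and no interim look stated, the plan shows no need for balance this tight, so the change is worth making as a cheap improvement.

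**What to change.** Make both changes; neither is sufficient alone.

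1. Remove the block sizes (or any imbalance limit) from the circulated protocol. Keep them in a restricted randomization file held by someone who does not recruit. Alone, this leaves the lagging-arm guess intact.
2. Regenerate the list without size 2. The preferred option is a big-stick scheme with limit 6, accepting that about 8% of allocations are forced and would be certain to anyone who knew the limit. Randomly mixed blocks of 4, 6 and 8 are a weaker alternative: they mainly remove the high-confidence guesses and cut the illustrative bias by only about a fifth.

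The cost is one new list, one new set of envelopes and a short deletion from the protocol. The arms may finish a few patients apart, at most 6 under the big stick, with power still about 90%.

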**Recruitment:** 

During pre-hospitalisation visit where surgical indications are established, eligible patients will

meet a research nurse who will explain the study giving patients oral and written information. If

the patient agrees to participate in the study, she will be included randomly in one of the two

groups after having signed a consent form. She will immediately be informed of her allocation to

the "Fast track" or the control group in order to best prepare her personal perioperative planning.

To increase the number of patients recruited, patients that meet the criteria of the study but who

were not informed during the pre-hospitalisation visit will be contacted by a research nurse after

the weekly colloquium of surgical indications, colloquium where all surgical indications of the

department of gynaecology of the HUG are confirmed.

**Intervention:** 

Two types of perioperative settings will be compared:

o Group 1: "Fast track" protocol

Group 2: conventional setting

1) "FAST TRACK" protocol

Preoperative evaluation and information:

o Patient information of the study during the pre-hospitalisation visit and patient consent to

participate in the study prior to hospitalization.

o Patient general health state optimization proposal prior to hospitalization:

Smoking cessation, if necessary (specialized consultation)

Weight loss, if necessary (nutrition consultation)

Patient autonomy and social environment evaluation (home care proposal if

necessary)

7

« Fast track » surgery on patient undergoing minimally invasive gynaecologic procedure : a randomized clinical trial. V2.0 – 2015.09.29

#### Preoperative strategy:

- Hospitalization on surgery day
- No prolonged fasting (solids stopped 6 hours before surgery and liquids encouraged up to two hours before surgery)

#### Perioperative strategy:

- o Anti-infectious prophylaxis: Cefazolin 2g IV
- o Pain control based on limited systemic opioid therapy use
- Anti-nausea prophylaxis: 4g Dexamethasone preoperative + 4mg Ondansetron postoperative
- o Fluid balance
- Anaesthesia via IV propofol / remifentanyl
- o Bladder catheter removal postoperative

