#### Postoperative strategy:

- o Pain control using balanced analgesia
- o Gum chewing
- o Antithrombotic prophylaxis by low-molecular-weight heparin (40mg/60mg, depending on patient weight, 6 hours post-op during entire hospital stay)
- Early oral refeeding (as of 4 h postoperative)
- Rapid mobilization (as of 4 h postoperative)
- Venflon removal 6 hours post-op
- o Standard criteria for hospital discharge the day after surgery, checked by a physician:
  - Lack of organ dysfunction (evaluated by physical examination)
  - > Afebrile condition
  - Simple effective analgesia
  - Normal feeding
  - Independent mobility
  - Patient consent
- o Planned outpatient follow-up: stitches/ skin staples removal on day 7, postoperative checkup on day 30
- o Home care if needed

The protocol will have to be well-known by surgeons, anaesthetists and the nursing team.

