### Perioperative strategy:

Treatments according to the surgeons and the anaesthesiologists practice:

- o Anti-infectious prophylaxis: Cefazolin 2g IV
- o Balanced anaesthesia via halogens gases

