#### Postoperative strategy:

- Mobilization depending on patient's general condition, on the evening of the surgery, at minimum 6 hours post operation
- Antithrombotic prophylaxis by low-molecular-weight heparin (40mg/60mg, depending on patient weight, 6 hours post-op during entire hospital stay)
- Same day refeeding, depending on the patient's general condition and according to her desire, proposed on the evening of the surgery at minimum 6 hours post operation
- o Bladder catheter and Venflon removal on day 1
- o Standard criteria for hospital discharge the day after surgery, checked by a physician:
  - ➤ Lack of organ dysfunction (evaluated by physical examination)
  - > Afebrile condition
  - > Simple effective analgesia
  - Normal feeding
  - Independent mobility
  - Patient consent
- Planned outpatient follow-up: stitches/ skin staples removal on day 7, postoperative checkup on day 30
- o Home care if needed

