#### Ethics:

The study protocol will be submitted to the ethics committee of the Geneva University hospital (HUG). If approval is given by the ethics committee, all patients with a surgical indication of laparoscopic hysterectomy for benign indication in the gynaecology department of the HUG will be proposed to participate in this study. Eligible patients will receive oral and written information by a research nurse. Study participation will be voluntary and participants will be free to withdraw from the study at any time. Written consent will be given before inclusion in the study.

To ensure patient confidentiality, once a patient accepts to participate in the study she will receive a study number on a first-come, first-served basis. For instance [name], 58th participant will be known under patient 58 irrelevant of whether she has been attributed to the protocol FT or conventional. This number will be written on the patient information and consent form, the medical staff case report, the care map and the patient's log-book. The document containing the name of the patient paired with her study number (la main courante) will be kept under lock at the clinical research unit of the gynaecology department. Only the investigators and the research nurses will have access to this document.

The patient information and consent form, the medical staff case report, the care map and the patient's log-book will also be kept at the clinical research unit of the gynaecology department where only the investigators and the research nurses will have access.

Study participation presents no particular risk for patients since the "Fast track" concept has already demonstrated efficiency in colorectal surgery with no morbidity increase. Moreover, the various stages of the "Fast track" protocol are already commonly applied on a case-by-case basis in our current conventional setting. The choice to exclude from the study patients needing an additional surgical procedure such as a prolapse surgery or urinary incontinence surgery as well as malignant pathologies is justified by the fact that operating time is prolonged which could compromise homogeneity of the sample. Non-French speaking patients will also be excluded from the study due to the necessity of their collaboration in filling a logbook drawn up in French on a daily basis during their hospitalization.

[figure not shown]

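### The Fast track arm lists preoperative dexamethasone as 4 g, not a plausible antiemetic dose and probably a slip for 4 mg; check the source page and correct the unit

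*Combined protocol and SAP*

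**What the plan says.** The Fast track protocol, under Perioperative strategy, gives the antiemetic regimen as "Anti-nausea prophylaxis: 4g Dexamethasone preoperative + 4mg Ondansetron postoperative". The two drugs on this line carry different units: grams for dexamethasone, milligrams for ondansetron.

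The Conventional setting protocol has no corresponding line. Its Perioperative strategy opens with "Treatments according to the surgeons and the anaesthesiologists practice" and then lists only the antibiotic and the type of anaesthesia.

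On how the text is used, the Fast track Postoperative strategy ends with "The protocol will have to be well-known by surgeons, anaesthetists and the nursing team". The Logistics section on collaboration between staff groups says of the gynaecology staff, and again of the anaesthetists, "A copy of the study protocol will be sent by e-mail"; the nursing team is to be informed in the same way.

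**The concern.** Dexamethasone at 4 g is not a credible single dose for preventing nausea. The line belongs to the current version of the protocol (V2.0) and forms part of the definition of the experimental arm, so it is an instruction to staff and not background. A reader who doubts the figure finds nothing elsewhere in the document to correct it.

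Three things are at stake:

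- **Patient safety.** Followed literally, the line would lead to a gross overdose.
- **Consistency with the ethics statement.** The Ethics section says that taking part carries no particular risk. A literal 4 g dose does not fit that statement.
- **Measurement of adherence.** The Instruments and Type of analysis sections provide for adherence to be assessed at each stage of the protocol. If the case report form copied the printed dose, a patient correctly given a milligram dose would count as a deviation. This is conditional, because the form is not part of the document.

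**Working it through.** No statistical formula applies. The check is a unit conversion and a search for any other statement of the dose.

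**1. Inputs from the document.** Fast track protocol, Perioperative strategy: "4g Dexamethasone preoperative" and, on the same line, "4mg Ondansetron postoperative".

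**2. Input that is assumed.** The document gives no reference or maximum dose for dexamethasone. A plausible single antiemetic dose is taken as 4 to 10 mg, from general clinical knowledge.

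**3. Size of the discrepancy.** Printed dose: 4 g × 1000 mg/g = 4000 mg. Ratio of printed to assumed intended dose:

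- intended 4 mg: 4000 / 4 = 1000
- intended 8 mg: 4000 / 8 = 500
- intended 10 mg: 4000 / 10 = 400

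The conclusion does not depend on which value in the range was meant.

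**4. Can the document correct itself?** Four drugs have a stated dose:

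| Drug | Fast track arm | Conventional arm | Cross-check |
|---|---|---|---|
| Cefazolin | 2 g | 2 g | agrees |
| Low-molecular-weight heparin | 40 mg/60 mg by weight | 40 mg/60 mg by weight | agrees |
| Dexamethasone | 4 g | not listed | none |
| Ondansetron | 4 mg | not listed | none |

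The heparin entry, "Antithrombotic prophylaxis by low-molecular-weight heparin (40mg/60mg, depending on patient weight, 6 hours post-op during entire hospital stay", appears in both arms and matches, as does cefazolin. Dexamethasone appears only once. The 4 mg beside it belongs to a different drug, so it suggests the intended unit but does not prove it.

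**5. Effect on the design.** The dose is not an input to the sample size of 85 per arm (170 in total), which rests on a difference of 0.5 standard deviations, 90% power and a two-sided 0.05 level. Correcting the unit leaves sample size, power and the cost comparison as they are.

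**The case against.** The strongest objection is that the printed page may be right. The text under review was read from a PDF by a program, and it shows small losses elsewhere: this line lacks the bullet character that the lines directly above and below it keep, and some entries in the reference list have no number. A missing letter m is therefore possible. Against that, the same line kept mg for ondansetron, and mg survived for heparin in both arms, so a loss at this one spot is less likely, though not excluded. The point stands as a reason to check the page before anything else.

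A second objection is that the document does not contradict itself, so the judgement that 4 g is wrong comes from outside it. That is true of the assumed range and of the resulting ratios. It does not rescue the printed figure, since no gram-level dose is credible for this use.

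A third is that harm is improbable and the matter is only typographical. The Ethics section says the stages of the pathway "are already commonly applied on a case-by-case basis in our current conventional setting". Logistics adds that anaesthetists are briefed orally and that a representative with Fast track experience is appointed. Staff also work from a signed care map, which is not shown and may already carry the right dose. All this supports a low probability of harm. It does not make an unsafe dose acceptable in text that defines treatment and is sent to those who give it.

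**Conclusion.** The concern holds. As written, the dexamethasone dose in the Fast track arm is wrong by a factor of 1000 if 4 mg was intended, and by 400 to 1000 over the assumed range of 4 to 10 mg. The error is one character in one line, and nothing else in the document corrects it.

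The conclusion rests on two assumptions: that the original page reads as the extracted text does, and that the intended dose is in the milligram range. The first can be settled by looking at the page. The second is safe as to the unit, but the exact figure needs clinical confirmation.

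Actual exposure to 4 g is not expected, and the trial's ability to answer its question is not affected. The line should be corrected because it would be unsafe if followed literally and correcting it costs almost nothing.

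**What to change.** 1. Look at the original protocol page. If it says 4 mg, no protocol change is needed.
2. If it says 4 g, ask the anaesthesia lead to confirm the intended dose, then change the unit to mg.
3. Check that the care map and the case report form state the same confirmed dose, so that adherence is judged against the right figure.
4. Re-circulate the corrected page to surgeons, anaesthetists and nurses.

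The cost is one page check, one confirmation, a one-character correction and an e-mail. Nothing in the design or analysis changes.
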